## Correlation between levels of biomarkers and disease progression

The results from our CSF biomarker studies suggest a correlation between levels of these cytoskeletal proteins and disease progression. Patients who progressed faster than -0.5 ALSFRS-R points per month had an average CSF tau level of 574 pg/ml, compared to an average level of 298 pg/ml in patients who progressed slower than -0.5 ALSFRS points per month ( $p=0.005$ ) (Figure 9). Levels of CSF pNFH showed a similar correlation to rate of clinical disease progression (Figure 10).

**Figure 9.** Patients with elevated levels of CSF tau at baseline predicted a more rapid decline based on change in ALSFRS-R scores ( $p=0.005$ )

**Figure 10.** Elevated levels of pNFH in the CSF at baseline was associated with a more rapid progression of disease as evidenced by change in ALSFRS-R scores per month ( $p=0.002$ ).

After 12 months of treatment with Memantine, patients showed a 27% decline in CSF tau ( $p=0.04$ ). (Figure 8) This contrasts with data from 10 untreated ALS patients that exhibited a

69% increase in median CSF tau levels over 18 months from 266 pg/ml to 451 pg/ml (**Figure 7**). Healthy control subjects showed no change in CSF tau levels over 12 months of follow up (**Figure 8**). Perhaps most intriguing was the finding that 27% of the patients corrected their CSF tau levels to that detected in healthy controls during the course of the therapy with Memantine and these patients showed a marked slowing in the progression of their disease to -0.42 ALSFRS-R points per month (**Figure 5**). These same four patients were followed in PNA clinic before enrollment in the trial and were losing on average -1.2 ALSFRS-R points per month prior to therapy.

### **Conclusions from Open Label Study**

The results from this trial suggest that the Memantine may slow down the progression of ALS. Another phase II study with Memantine was completed by a group in Portugal who studied 60 patients in a blinded placebo-controlled study which did not illustrate benefit in slowing disease progression. This study; however, did not analyze CSF and due to its small size the power only 80% to detect a 50% decline (30). Despite these conflicting results we believe the pilot trial data and the scientific background behind Memantine indicate that a placebo-controlled trial using higher doses of Memantine should be undertaken in order to evaluate the possibility that Memantine may have a positive effect on this universally fatal disease.

The data from the open label trial suggests that ALS patients could be stratified based on the level of tau and pNFH in their CSF. We will also examine whether the pNFH/C3 ratio can be correlated with disease progression. Patients' CSF could be analyzed at baseline and this could be used to stratify them into treatment arms with an equal number of slow and fast progressors in each arm. If a robust diagnostic biomarker for ALS was found, it would accelerate and simplify the investigative process and result in the earlier implementation of appropriate therapies.

Despite extensive research into new therapeutic modalities for ALS, the disease remains universally fatal with an average life expectancy of 2-5 years. Data presented in the preliminary results section suggests that patients with ALS treated with Memantine at 10 mg BID and Riluzole demonstrated significant slowing of their disease progression compared to their baseline rate of progression while on Riluzole alone. A concurrent phase II study performed by [name]; however, found no effect in a randomized placebo-controlled study of 60 patients. Nor did the Carvalho study examine the potential that a higher dose of Memantine might be effective (30). We believe that both trials established that 10

mg BID is a safe and tolerated dose in ALS patients. There are numerous studies of Memantine in other disease states at doses up to 60 mg a day that show good tolerability (31-34). The majority of side effects that were seen were dizziness, headache, fatigue and nausea. Therefore, this study will test whether a higher dose of Memantine, 20 mg BID would have a more significant slowing on disease progression in a randomized placebo-controlled Phase IIB trial. We feel the scientific background of Memantine with numerous proposed mechanism that could benefit ALS patients, and the results of our open label pilot trial, warrant studying Memantine at a higher dose to see if an effect can be demonstrated in a placebo-controlled trial.

The dose of 20 mg BID of Memantine has been studied in major depressive disorder, tension headache, bipolar disorder, nystagmus, diabetic neuropathy, and tremor. These studies found that dizziness, headache, fatigue, and nausea were the most common side effects. There were no clear drug related serious side effects seen in these studies to raise significant concern about using such a dose in a study of ALS patients. Discontinuation rates tended to be higher in patients on active drug and dizziness was the most common adverse event seen occurring in 20-25 percent of patients. These studies indicate that Memantine has been studied and shown to be safe even at doses as high as 60 mg a day; therefore we feel that ALS patients will tolerate 40 mg a day; however as stated in the tapering section of this proposal, patients will have options to down titrate if necessary.

The primary outcome measure will be disease progression as measured by the number of points lost on the ALS Functional Rating Scale- Revised (ALSFRS-R) during the 36 weeks of therapy. The patient's rate of progression on active therapy during the 36-week treatment arm will be compared to the rate of progression of the placebo arm. We will also attempt to enrich the placebo group data from historical controls from previous ALS studies. Disease progression in numerous ALS clinical trials has been measured using the ALSFRS-R which is a 12 question rating scale used to determine each participant's assessment of their capability and independence in daily activities. The ALSFRS-R can be administered with high inter-rater reliability and test-retest reliability in person or over the phone. The advantages of using such a measurement to determine disease progression are that the categories are relevant to ALS, it is a sensitive and reliable tool, and the rate of decline correlates strongly with survival (27, 28).

## **II. Research Plan and Design**

### **A. Study Objectives**

This study is designed to not only validate the preliminary data that Memantine can significantly slow down the course of ALS but to also determine if Memantine can improve ALS patients who illustrate characteristics of FTD. We also hope to establish the foundation for conducting future clinical trials in ALS by providing prospective blinded data for the utility of biomarkers as novel outcome measures that may more rapidly assess the efficacy of future drugs.

### **B. Study Type and Design**

This is a phase IIB multi-centered double blind, placebo-controlled study evaluating the safety and efficacy of Memantine at 20 mg BID in patients with ALS. 90 participants will be recruited from 14 centers in the United States. Sites were chosen based on their ALS research experience and with the help of the Western Amyotrophic Lateral Sclerosis (WALS) database. The sites that we have chosen to participate are active ALS centers who have years of ALS research experience. WALS has experience as a central coordinating center and has data management personnel and a leading biostatistician. The clinical evaluators, who gather efficacy data, are highly trained and standardized. They are experienced in ALS study details and standards.

The steering committee for this study consists of [name]. (PI), [name] (Co-PI), [name] (Co-I) [name], [name]. (Biostatistician), and [name], CCRP (Project Manager).. The external medical monitor for this study is [name]. The Data and Safety Monitoring Board is comprised of [name] (Chair), [name] MD, [name] MD, [name] MD, and [name] PhD.

The University of Kansas Medical Center will be the Outcomes and Monitoring Center of the study. This will include the training of the study site evaluators and the validation of secondary outcome measures (FVC, ALSFRS-R, ALS-CBS, NPI-Q, C-SSRS) with ongoing effort in monitoring quality assurance and test-re-test reliability. The University of Kansas Medical Center will provide ongoing quality assurance of all clinical monitoring duties and clinical monitoring responsibilities for the study.

## **C. Sample Size, Statistical Methods, and Power Calculation**

### *Sample size*

90 patients will be randomized in a 2:1 ratio to either Memantine, 20 mg BID or placebo. The active and placebo will be over encapsulated by the research pharmacy at the University of Iowa Research Pharmacy. Medication will be dispensed at 10 mg and placebo kits that are blinded to the investigator and the patient. After the patient fulfills screening criteria, data entered into the database, and their screening visit is monitored remotely, the patient will be randomized using a predetermined randomization formula. KUMC will provide the site with proper kit numbers for each randomized patient. All randomized patients will be instructed to take one capsules once a day for the first two weeks from a blinded bottle that contains the 10 mg capsules or matching placebo. At week three, patients will be instructed to take one capsule twice a day. At week five, patients will be instructed to take one capsule in the morning and 2 capsules in the evening. At week seven, patients will be instructed to take two capsules twice a day. Patients will remain on this dose for the remainder of the study; unless they cannot tolerate the dose. If this is the case, they will follow the proper dosing taper (see dosing reduction/discontinuation section).

### *Statistical Methods*

The primary comparison for efficacy will be based on a linear mixed effects (lme) model fit to the ALSFRS-R data for the 90 patients followed over 36 weeks. The model will be used to calculate fixed effects for intercept, placebo slope (rate of decline of ALSFRS-R) and change in slope for those treated with Memantine. Random effects included are for individual patient variation in intercept, slope and random error at each time point. The test for treatment effect is based on the change in slope due to treatment, as estimated by the model. Testing for significance is two-sided at a 10% level of significance. Analysis is limited to patients who receive at least one treatment dose and have at least 2 measurements (one at baseline and one after treatment). Deaths are treated the same as drop-outs. This model weighs each patient inversely by his estimated variance so that patients with missing values receive less weight than those with complete data.

We will also attempt to enrich the placebo group with historical controls with matching patients from the historical placebo database of 715 patients added to the 30 placebo patients from this trial. The historical controls will be selected to have same entry criteria as patients in this trial. There will be no patient-by-patient matching. We will first test whether the 30 patients from this trial differ from those in the historical database (using the same model with a term added to identify source: historical or contemporary). If this test finds that the two placebo groups differ, historical control will not be added and the combined placebo vs treated test will not be conducted. If the placebo control sets do not differ, the lme model described above will be fit to the combined data.

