We propose that therapies to reduce axonal injury would reduce pNFH and/or NF-L levels in the blood and correlate to a reduction in neuronal cell death and increased patient survival. The prior data from a phase II trial for Memantine in ALS patients indicated that reductions in CSF tau levels correlated to slowing of disease progression (2). Sussmuth et al demonstrated that elevated levels of CSF tau were found in patients with ALS (1); however, other studies have not found a strong correlation (16). Therefore, we will not examine tau levels in our current clinical trial.

We feel there is a significant body of literature to support the fact that pNF-H, NF-L, chitinase-1 (Chit-1) and TNF- $\alpha$  may be sensitive biomarkers for neurodegeneration and activation of glial cells and inflammation during ALS. Studies related to neurofilament were noted above. Cereda and colleagues demonstrated that ALS patients exhibit elevated levels of TNF- $\alpha$  and soluble TNFR receptor in the plasma (17). Recent studies have indicated that the chitinase Chit-1 is elevated in the CSF of ALS patients and denotes microglial activation in the spinal cord (18). We also detect significantly increased levels of Chit-1 in the plasma of ALS patients when compared to controls (**Figure 4**).

[figure not shown]
More importantly, we believe based on the open label trial and other previously mentioned studies, that the blood levels of these biomarkers may predict rate of disease progression and monitor effectiveness of Memantine during our upcoming clinical trial. This would offer a number of potential benefits if found to be true. It would allow for a better stratification in future clinical trials as equal number of fast and slow progressors could be randomized into each arm of future studies. This may negate a potential bias against an effective drug if too many rapid progressors are randomized into the active arm. We also believe that if an effective therapy for ALS is found that there may be observed changes in the levels of the blood biomarkers and that these changes may occur as early as four to six months. Therefore, we propose to study the levels and ratios of these

biomarkers at screening and at multiple times during the trial to see if response to therapy can be correlated with rate of disease progression as our preliminary work suggested.

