## **Results of Open Label Trial**

Memantine, an FDA approved agent for the treatment of Alzheimer's disease, has been thought to reduce the effects of glutamate mediated excitotoxicity (19). It may also inhibit and reverse the abnormal hyperphosphorylation of tau, which leads to its sequestration in neuronal intracellular inclusions (20). In addition, Memantine has been shown to prolong survival in a transgenic mouse model of amyotrophic lateral sclerosis (21). Based on the potential for Memantine to alter the course of the disease in ALS patients, Phoenix Neurological Associates conducted a 20 patient, open label pilot trial of Memantine given at 10 mg bid, in patients taking Riluzole. The data suggested that Memantine might have significant clinical benefit in patients with ALS.

19 patients completed more than 3 months of therapy, 16 patients completed 6 months of therapy and 12 patients completed the entire 18 months of the study. Patients were evaluated based on the number of points lost per month on the ALS Functional Rating Scale - Revised (ALSFRS-R). The ALSFRS-R is a validated measure of ALS disease progression and is a predictor of survival that is typically used as an accepted outcome measure in ALS clinical trials (27, 28). As this was an open-label trial, patients were compared to historical controls and a subset of patients were compared to their pre-study rate of progression. Numerous placebo-controlled studies in ALS have shown that patients on Riluzole, or on no therapy, lose on average -0.9 ALSFRS-R points per month (29).

[figure not shown]
A linear mixed effects model was used to compare rates of decline for the 20 patients taking Memantine with 415 placebo patients from previous clinical trials. This natural history model (from 8 previous clinical trials) estimated a slope of -0.89 (95% CI -0.95 to -0.83) for placebo and -0.55 (95% CI -0.95 to -0.15) for Memantine treated patients (two-sided  $p=0.10$  for the treatment effect). This represents a 38% reduction in slope in this small sample.

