In addition, 12 of these patients were followed in clinic before beginning the pilot trial. Therefore, PNA had an established baseline rate of disease progression for these patients, which was -1.07 ALSFRS-R points per month (**Figure 5**). Since study conclusion, 8 patients have remained on Memantine. These patients have averaged 28 months on Memantine treatment and have progressed at only -.48 points per month. Thus, compared to their own baseline disease progression or to placebo controls, patients who began Memantine therapy showed a marked drop in their rate of disease progression.

[figure not shown]

**Figure 5.** Illustrates historical ALS control patients on Riluzole lose on average, -0.9 pts per month, whereas the patients that were analyzed from the pilot trial lost an average of -0.55. Patients whose tau levels corrected to within the normal range lost -0.42 points per month. This group of 4 patients was losing -1.2 points a month prior to treatment.

[figure not shown]
**Biomarker Studies** The patient's CSF, at baseline, 6, and 12 months of Memantine therapy, was analyzed. Compared to healthy control subjects, the levels of tau and phosphorylated neurofilament heavy chain (pNF-H) at baseline were significantly higher in the patients with ALS ( $p=0.038$ ) (**Figure 6**). It was previously determined that the levels of CSF tau and pNF-H increase over time in untreated ALS patients, perhaps reflecting ongoing neuronal death (**Figure 7**). In contrast, ALS patients treated with Memantine showed a decrease in average CSF tau levels over 12 months of therapy ( $p=0.04$ ) (**Figure 8**), while healthy untreated control subjects do not exhibit a change in CSF tau levels over time.

**Figure 6.** Compared to healthy control subjects, the levels of tau at baseline were significantly higher in patients with ALS enrolled in our pilot trial.

[figure not shown]
**Figure 7.** ALS patients who were not treated with Memantine show an increase in their levels of tau and pNF-H over two year

[figure not shown]
**Figure 8.** There is a decline in tau levels in ALS patients treated with 12 months of Memantine compared to healthy (normal) controls.

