#### *Statistical Power*

We used data from our historical placebo to estimate power for both the test that uses only patients enrolled in the trial and the test where historical placebo is added. To accomplish this we first randomly sampled 75 placebos from our database. The first 30 are assigned as placebo and their ALSFRS-R values are unchanged. The remaining 60 have their slopes reduced by a fixed percentage of their lme estimated slope and the random error is added back in to simulate real measurements. Next, we test for a treatment effect in the simulated dataset of 90. The simulated data are then combined with the remaining (unsampled) placebo and tested for difference in the placebo subgroups. If this test is not significant (at two-sided  $p<0.05$ ), the combined data are tested for a treatment effect. This procedure was carried out 1000 times, noting the p-values from each simulation. Power was estimated by counting the number of times p-values were less than 0.1 (two-sided test).

These simulations with a treatment effect set to 40% show that with 90 patients at a 2:1 ratio of Memantine to placebo, power was 82% for the test that uses only the 90 patients simulated to be in the trial. Adding historical placebo boosted the power to over 90%.

Because there is a great deal of clinical variability among patients with ALS the major drawback to this study is its small size. A previous study looking at 60 ALS patients performed by Carvalho et al, found no significant improvement in patients randomized to 10 mg BID of Memantine compared to placebo (30). This contradicts the data from our pilot study in which patients' rate of progression was compared both to historical controls and their own baseline rate

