of progression. Since it is impossible to identify if a patient is a fast or a slow progressor at randomization, small studies such as Carvalho's, or our previous pilot open label trial, can be skewed if a group of slow progressors are randomized to a placebo arm or a group of fast progressors are randomized to an active arm. We have attempted to modulate these effects somewhat by excluding patients who have had the disease for more than three years as possibly being slow progressors. In addition, we have excluded patients with significantly impaired FVC's, to try to limit the number of fast progressors. These measures are very standard in current ALS trials. Another limiting factor to both Carvalho's and our pilot study is that neither study analyzed the efficacy of Memantine at a higher dose. We feel that by using a higher dose of Memantine a more efficacious response may be seen even in a study which is relatively small. Another limitation to this study is 20mg/bid of Memantine has not been studied in ALS patients. Although 40, 50, 60 and even 80mg/d of Memantine have been studied in numerous other disease states and have been shown to be safe and tolerated, it is still unknown how this population will respond. However, we will assess carefully for safety and adverse events.

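### The primary mixed model is valid but has no prognostic covariate for slope; prespecifying an approximate pre-study progression rate is a cheap, modest improvement

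*Combined protocol and SAP*

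**What the plan says.** Statistical Methods specifies "fixed effects for intercept, placebo slope (rate of decline of ALSFRS-R) and change in slope for those treated with Memantine". On the random part it says: "Random effects included are for individual patient variation in intercept, slope and random error at each time point". It does not say whether the random intercept and slope may be correlated. The Sample size and Randomization sections refer to a formula fixed in advance and name no stratification factor.

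Statistical Power concedes that "the major drawback to this study is its small size" and warns that small studies can be distorted when fast or slow progressors fall unevenly between arms. Its argument opens "Since it is impossible to identify if a patient is a fast or a slow progressor at randomization". The remedy it offers is entry limits on disease duration and FVC. Stratifying by progression is left to later trials, where an "equal number of fast and slow progressors could be randomized into each arm of future studies".

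Statistical Methods also plans to add historical placebo patients, after a check: "We will first test whether the 30 patients from this trial differ from those in the historical database".

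Several sections bear on whether a pre-study rate is available. Study Population and the Exclusion Criteria limit time since onset to three years. Visit 1-Screening and the Study Table record ALSFRS-R at screening. For 12 pilot patients, "PNA had an established baseline rate of disease progression for these patients". Reference 28 is a study of progression rate at diagnosis.

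**The concern.** The plan names a specific threat, and its model contains nothing aimed at it. Entry limits narrow the population but do not balance 60 patients against 30. The stated reason for doing no more is stronger than the rest of the protocol supports, because a rough rate, points lost since onset divided by months since onset, can be computed for each patient at screening.

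At stake is the credibility of the estimate in an unlucky randomization. The standard error already allows for chance imbalance, but the imbalance still moves the estimate. If the memantine arm happened to start with faster progressors, the result would face the criticism that the protocol makes of earlier small studies.

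**Working it through.** **Inputs from the documents.** 60 memantine and 30 placebo patients; two-sided 10% test; 40% slope reduction; placebo slope -0.89 points/month, 95% CI -0.95 to -0.83, from 415 patients (Results of Open Label Trial); ten ALSFRS-R scores (Study Table).

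**The plan's own power.**
- SE of placebo slope = (0.95 - 0.83)/(2 × 1.96) = 0.0306
- Per-patient slope SD = 0.0306 × √415 = 0.624
- Target effect = 0.4 × 0.89 = 0.356
- SE of difference = 0.624 × √(1/60 + 1/30) = 0.139
- Power = Φ(0.356/0.139 - 1.645) = 81.8%, against the stated 82%

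Rounding of the CI limits alone allows an SD of 0.572 to 0.676, and so power from 87% down to 76%.

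**Unit of imbalance.** Below, one chance SD is the SD of the between-arm difference in mean pre-study rate under randomization: √(1/60 + 1/30) = 0.22 patient SDs. A difference above one chance SD against memantine has probability 1 - Φ(1) = 16%, about one trial in six.

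**Simulation of the mixed model.** The planned model was fitted by REML with correlated or independent random effects, then refitted with the pre-study rate and rate-by-time added. Dropout was 25% by week 36. It was interpolated from the pilot ("16 patients completed 6 months of therapy and 12 patients completed the entire 18 months of the study", of 20): 36 weeks is 8.3 months, so 20% + (2.3/12) × 20% = 24%, rounded up. Assumed, because the documents do not give them: scale maximum 48, residual SD 2.0, 6 to 36 months since onset, a lognormal pre-study rate, true slope SD 0.525 (set to give about 82% power), a constant effect of 0.356, and R² itself. There were 2,500 trials per main setting.

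| R² | Planned, correlated | Planned, independent | Adjusted | Gain over correlated | Gain over independent |
|---|---|---|---|---|---|
| 0% | 82.6% | 82.4% | 81.8% | -0.8 | -0.6 |
| 4% | 81.1% | 79.5% | 81.4% | +0.4 | +1.9 |
| 10% | 82.0% | 81.2% | 83.8% | +1.7 | +2.6 |
| 20% | 82.5% | 79.2% | 85.7% | +3.2 | +6.5 |

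The Monte Carlo SE of the gain over the correlated version is 0.3 to 0.5 points. With a 3-month SD recall error in onset date, that gain is +0.8 at R² 10% and +2.2 at 20%. With the effect a fixed percentage of each slope, as in the plan's own power simulation, it is +0.2 at R² 10% (SE 0.5).

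**Trials with more than one chance SD against memantine.**

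| R² | Planned, correlated | Planned, independent | Adjusted |
|---|---|---|---|
| 4% | 75% | 70% | 80% |
| 10% | 76% | 70% | 85% |
| 20% | 72% | 57% | 84% |

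The SE is about 2 points. A simpler simulation of per-patient slopes gives 74, 67 and 57% unadjusted, against 82, 84 and 87% adjusted.

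**Shift in the estimate per chance SD of measured rate**, at R² 4, 10 and 20%: 0.014, 0.026, 0.040 (correlated), which is 4, 7 and 11% of 0.356; 0.023, 0.040, 0.059 (independent), which is 6, 11 and 17%; and 0.001 or less in size when adjusted. The closed form √R² × 0.139 gives 0.028, 0.044, 0.062, close to the independent version.

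**Imbalance in true progression.** Adjustment removes about R² of it. With the rate built from the screening score (observed correlation with slope 0.13 to 0.43), simulation removed 3 to 29%.

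**Validity.** Under no effect at R² 10%, rejection was 11.0% (correlated), 10.0% (independent) and 10.7% (adjusted), against a nominal 10% (SE 0.6), with the screening score serving both as first outcome and in the covariate.

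**The historical-placebo check.** With all 715 controls and a two-sided 5% test, SE = 0.624 × √(1/30 + 1/715) = 0.116. The skew detectable with 80% power is 2.80 × 0.116 = 0.33 points/month, 92% of the target effect. For a skew of one SE of the placebo mean, 0.624/√30 = 0.114, power is about 16%.

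**The case against.** A reader might infer that the planned test is biased, or that adjustment would largely remove a fast/slow imbalance. The documents support neither. Randomization and the standard error already cover chance imbalance, and the simulated type I error is close to nominal. The covariate balances only the measured rate: at R² of 4 to 20%, some 80 to 96% of slope variance stays unexplained, so much of what the protocol fears would remain.

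The planned combined analysis also helps. If its check passes and all 715 controls enter, the 30 trial placebos are 30/745 = 4% of the pooled group, and the variance factor falls from 1/60 + 1/30 = 0.050 to 1/60 + 1/745 = 0.018. A placebo-arm skew is then mostly diluted. This stands, but it does nothing for a skew in the memantine arm, and the controls are not randomized.

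R² is unknown. The pilot rates came from clinic follow-up, not from a recalled onset date, and the title of reference 28 concerns survival. The average gain is smaller than the uncertainty in power from CI rounding. If random effects may correlate, the planned model already uses part of the baseline score. All of this stands, and it makes the point optional. That no onset-date field is listed carries little weight, since medical history is taken and the case report form is not in the documents.

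**Conclusion.** The point holds as a low-cost improvement to consider, with medium confidence. The primary model is valid (leaving aside the handling of deaths as drop-outs, a separate matter), but it omits a prognostic covariate that the trial could compute, for a threat that the protocol itself names. The average power change is about -1 to +3 points against correlated random effects, up to about +7 against independent ones, and near zero at R² 10% under a fixed-percentage effect. The worthwhile benefit is protection in the one trial in six with an unfavourable measured rate. These sizes rest on the assumed R² of 0 to 20% and on the simulation settings listed above.

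**What to change.** Before unblinding:

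1. Prespecify in the trial-only primary model the pre-study rate = (scale maximum minus screening ALSFRS-R) / months from onset to screening, as a main effect and by time. The by-time term is the one that adjusts the slope. State the scale maximum, and that the screening score is also the first outcome, since the Study Table shows no ALSFRS-R at the baseline visit.
2. Use one definition of onset (Study Population refers to symptoms, the Exclusion Criteria to weakness) and give a rule for missing dates.
3. Keep the unadjusted model as a sensitivity analysis.
4. Adjust the combined analysis only if the historical records hold onset date and baseline score; otherwise state that the two models differ. If those fields exist, R² can be estimated from them first.
5. Optional: state whether random intercept and slope may correlate, and soften the claim that progressor type cannot be identified.

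The cost is an explicit onset-date field, if the case report form lacks one, and SAP wording for one covariate and its time interaction, with no new visits or assays. The downsides are reliance on a recalled date, up to about 1 point of power if the covariate is uninformative, and possibly different models for the trial-only and combined analyses.
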